1. PROTOCOL SUMMARY

1.1 Synopsis

Title: Phase 2 Clinical Trial to Optimize Immune Coverage of SARS-CoV-2 Existing and Emerging Variants

Short title: COVID-19 Adaptive VAriant Immunologic Landscape Trial (COVAIL Trial)

Phase: Phase 2

Population: Approximately 1,500 healthy individuals aged \geq 18 years

Sites: Up to 30 US clinical research sites

Rationale:

The Severe Acute Respiratory Syndrome Coronavirus 2 (SARS-CoV-2), causative agent of the coronavirus disease of 2019 (COVID-19) pandemic, has infected close to 600 million people worldwide and resulted in more than 6 million deaths, including 1 million deaths in the United States (August 18, 2022 WHO; www.who.int). As of September 2022, there are four approved or authorized vaccines in the U.S.: two using mRNA-based technology (Pfizer BioNTech [BNT162b2] and Moderna [mRNA-1273]), one using a non-replicating viral vector vaccine (Johnson and Johnson adenovirus Ad26), and one using protein adjuvanted vaccine (Novavax) all encoding the spike protein of the ancestral strain. A fifth manufacturer Sanofi has another adjuvanted protein vaccine that showed efficacy in a phase 3 trial. These and other WHO authorized vaccines have been an essential countermeasure against the pandemic.

However, the emergence of many variants of concern with different degrees of immune escape challenge the effectiveness of these vaccines. The persistent evolution of the virus leads to the consideration of adapting vaccines to antigenically match circulating variants as well as expanding and optimizing immune coverage to existing and emerging antigenic variants. Current efforts are directed towards modifying the existing vaccines to include the current circulating variant Omicron. However, Omicron may not be the circulating variant during the next wave of COVID-19. It is important to look beyond Omicron and understand the immunologic landscape and how we can use prototype and variant vaccines alone or in combination to address emerging variants.

This phase 2 clinical trial will evaluate the safety and immunogenicity of additional doses of prototype and variant (alone or in combination) vaccine candidates in previously vaccinated participants with or without prior SARS-CoV-2 infection, and will evaluate innate, cellular, and

humoral immune responses to inform on how to shift the immune response to cover new variants as they emerge.

Objectives:

Primary:

To evaluate humoral immune responses of candidate SARS-CoV-2 variant vaccines, alone or in combination.

Secondary

1. To evaluate the safety of candidate SARS-CoV-2 variant vaccines, as assessed by:
 - Local and systemic solicited Adverse Events for 7 days following each vaccine dose.
 - Unsolicited Adverse Events from Dose 1 to 28 days following each vaccine dose.
 - SAEs, MAAEs, AESIs, NOCMCs, and AEs leading to withdrawal from the study from Dose 1 to 12 months after last vaccine dose.

Exploratory:

1. To assess, in at least a subset of samples, the B cell immune response of candidate SARS-CoV-2 variant vaccines.
2. To assess, in at least a subset of samples, the SARS-CoV-2 spike protein-specific T cell responses of candidate SARS-CoV-2 variant vaccines.
3. To assess, in at least a subset of samples, the magnitude, phenotype, and percentage of innate immune cells with candidate SARS-CoV-2 variant vaccines.
4. To assess, in at least a subset of samples, the functional potential of SARS-CoV-2 specific antibodies to mediate Fc-effector functions across candidate SARS-CoV-2 variant vaccines.
5. To evaluate breakthrough SARS-CoV-2 infection by sequencing strains for variant spike lineage and assessing anti- nucleocapsid serology.

Study Design:

This is a Phase 2 randomized open label, non-placebo controlled, multi-site, multi-stage clinical trial in individuals, 18 years of age and older, who are in stable state of health, have received a complete authorized/approved vaccine series (primary series + a booster either with homologous or heterologous vaccine products) \geq 16 weeks prior to enrollment.

Subjects will be stratified by i) age (18-64 years and \geq 65 years of age) (however arms 16 and 17 or stage 4 will only enroll participants between the ages of 18-49 years) and ii) history of confirmed prior SARS-CoV-2 infection, and randomly assigned to receive one of several variant vaccines. Enrollment will target a goal of approximately 45% of each of the variant vaccine arms to be in

older adults (≥ 65 years of age) for stages 1, 2 and 3 and approximately 20% to have had confirmed COVID-19 for all 4 stages.

This is an adaptive design and may add arms of new vaccine platforms and/or variant lineage spike vaccines as needed. The study arms will be conducted in different stages (that could overlap) depending on public health needs and availability of study products (starting with the available mRNA vaccines).

Table 1: Study Arms

	Arms	Vaccine Platform	Sample Size	Vaccine Candidate	Interval (weeks)*	Timing of First Dose	Timing of Second Dose
Stage 1	1	Moderna mRNA-1273	100	Prototype	≥ 16	D1	NA
	2		100	Beta + Omicron	≥ 16	D1	NA
	3		100	Beta + Omicron	≥ 16	D1	D57
	4		100	Delta + Omicron	≥ 16	D1	NA
	5		100	Omicron	≥ 16	D1	NA
	6		100	Omicron + Prototype	≥ 16	D1	NA
Stage 2	7	Pfizer/ BioNTech BNT162b2	50	Wildtype (Prototype)	≥ 16	D1	NA
	8		50	Beta + Omicron	≥ 16	D1	NA
	9		50	Omicron	≥ 16	D1	NA
	10		50	Beta	≥ 16	D1	NA
	11		50	Beta + Wildtype	≥ 16	D1	NA
	12		50	Omicron + Wildtype	≥ 16	D1	NA
Stage 3	13	Sanofi CoV2 preS dTM-AS03	50	Prototype	≥ 16	D1	NA
	14		50	Beta	≥ 16	D1	NA
	15		50	Beta+ Prototype	≥ 16	D1	NA
Stage 4	16^	Pfizer/ BioNTech BNT162b2 bivalent	100	Omicron BA.1 + Wildtype (Prototype)	≥ 16	D1	NA
	17^		100	Omicron BA.4/BA.5 + Wildtype (Prototype)	≥ 16	D1	NA

Two age strata:

- 18-64 years
- ≥ 65 years (~45% in ≥ 65 years).

^For arms 16 and 17 or stage 4, only participants between the ages of 18 to 49 years will be enrolled.

Two infection strata:

- Confirmed prior SARS-CoV-2 infection (~20%)
- No known history of prior infection.

*interval (in weeks) since last exposure to SARS-CoV-2 infection or vaccination

Duration of Study: Up to 4 years

Duration of participation per subject: Up to 2 years (approximately 12 months after last inoculation)

Criteria for Inclusion/Exclusion:

Inclusion Criteria:

Participants must meet all of the following criteria to be eligible to participate in this study:

1. Individuals \geq 18 years of age at the time of consent (18-49 years for stage 4).
2. Confirmed receipt of a complete primary and booster COVID-19 vaccine series, either homologous or heterologous, with an FDA authorized/approved vaccine at least 16 weeks prior to study vaccine dose 1.
3. Willing and able to comply with all scheduled visits, vaccination plan, laboratory tests and other study procedures.
4. Determined by medical history, targeted physical examination and clinical judgement of the investigator to be in stable state of health.

Note: Participants with pre-existing stable chronic medical conditions defined as condition not requiring significant change in therapy or hospitalization for worsening disease within 4 weeks from enrollment, can be included at the discretion of the investigator.

Exclusion Criteria:

Participants meeting any of the following criteria will be excluded from the study:

1. Confirmed SARS-CoV-2 infection $<$ 16 weeks prior to any study vaccine dose.
2. Pregnant and breastfeeding participants.
3. Prior administration of an investigational coronavirus vaccine at any time or SARS-CoV-2 immunoglobulin, monoclonal antibody or plasma antibody therapy in the preceding 3 months.

Note: subjects that participated in clinical trials of products that are now FDA approved/authorized are allowed to participate.

4. Current/planned simultaneous participation in another interventional study or receipt of any investigational study product within 28 days prior to vaccine study dose(s).

5. A history of anaphylaxis, urticaria, or other significant adverse reaction requiring medical intervention after receipt of a vaccine, polyethylene glycol (PEG), polysorbate or nanolipid particles.
6. A history of myocarditis or pericarditis at any time prior to enrollment (for subjects in stages 1, 2 and 4).
7. Received or plans to receive a vaccine within 28 days prior to or after any dose of study vaccine.

Note: Receipt of seasonal influenza vaccine is allowed at any time.

8. Bleeding disorder diagnosed by a healthcare provider (e.g., factor deficiency, coagulopathy, or platelet disorder requiring special precautions) or bleeding difficulties with intramuscular injections or blood draws.
9. Current or previous diagnosis of an immunocompromising condition or other immunosuppressive condition.
10. Advanced liver or kidney diseases.

11. Advanced (CD4 count < 200) and/or untreated HIV, untreated Hepatitis B or untreated Hepatitis C.

12. Received oral, intramuscular or intravenous systemic immunosuppressants, or immune-modifying drugs for >14 days in total within 6 months prior to any study vaccine dose (for corticosteroids \geq 20 mg/day of prednisone equivalent).

Note: Topical medications are allowed.

13. Received immunoglobulin or blood-derived products, within 3 months prior any study vaccine dose.

14. Received chemotherapy, immunotherapy or radiation therapy within 6 months prior to any study vaccine dose.

15. Study personnel or an immediate family member or household member of study personnel.

16. Is acutely ill or febrile 72 hours prior to or at vaccine dosing (fever defined as \geq 38.0°C/100.4°F). Participants meeting this criterion may be rescheduled within the relevant window periods.

Note: Afebrile participants with minor illnesses can be enrolled at the discretion of the Investigator, as long as the illness is not suggestive of COVID-19.

17. Plan to receive a COVID-19 booster vaccine outside of the study within the next 180 days. (for subjects in Stage 4 only)

Safety

- Solicited Adverse Events will be collected for 7 days following each vaccine dose.

- Unsolicited Adverse Events will be collected from Dose 1 to 28 days following each vaccine dose.
- SAEs, MAAEs, AESIs, NOCMCs, and AEs leading to withdrawal from the study will be collected from Dose 1 to 12 months after last vaccine dose.
- The study will use halting rules for vaccination. See [Section 7.1](#) for details.

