2.2.2 Known Potential Benefits

On March 29, 2022, the FDA authorized an additional booster dose (fourth dose) of mRNA vaccine for adults 50 years of age or older and adults with immunocompromising conditions. Subsequent to this authorization, the CDC updated its guidance to permit an additional booster dose for these groups, acknowledging the potential benefit of a second booster for those at risk for severe COVID-19 illnesses as well as for those who received two doses of the Johnson & Johnson vaccine. The exact benefit of this second booster dose is difficult to ascertain given the design of the studies supporting these recommendations. Variant specific mRNA vaccine candidates have been shown to induce similar D614G antibody responses as the prototype mRNA vaccine (i.e. back boost). Therefore, receipt of a variant vaccine in this study is not expected to be inferior to any benefits received from a second booster dose of a Pfizer or Moderna mRNA vaccine obtained outside this trial (i.e. is not inferior to standard care). The Sanofi/GSK COVID-19 vaccine is not yet FDA authorized; the potential benefit of a booster dose is unknown.

On August 31th, 2022, the FDA amended the EUAs of the Moderna COVID-19 Vaccine and the Pfizer-BioNTech COVID-19 Vaccine to authorize bivalent formulations of the vaccines for use as a single booster dose at least two months following primary or booster vaccination. The updated bivalent booster vaccines contain two mRNA components that code for 2 different Spike proteins of SARS-CoV-2 virus, one for the original or “prototype” strain Spike protein, and the other for

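### Inclusion Criterion 2 does not enforce the 16-week interval since last vaccination stated in Table 1: an authorized further booster 29 to 111 days before Day 1 meets every criterion as worded

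*Protocol*

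**What the plan says.** Section 1.1, Table 1, gives an interval of at least 16 weeks for every arm. Its footnote defines this as the "interval (in weeks) since last exposure to SARS-CoV-2 infection or vaccination". Section 4.2 presents the four-month spacing as a deliberate design choice.

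The eligibility criteria in the same section treat the two kinds of exposure differently:

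- **Infection.** Exclusion 1 bars a confirmed infection less than "16 weeks prior to any study vaccine dose".
- **Vaccination.** Inclusion 2 requires "Confirmed receipt of a complete primary and booster COVID-19 vaccine series, either homologous or heterologous, with an FDA authorized/approved vaccine at least 16 weeks" before study dose 1. The study design text describes that series as "primary series + a booster either with homologous or heterologous vaccine products", with the booster in the singular.
- **Other limits on past vaccines.** Exclusion 7 bars anyone who "Received or plans to receive a vaccine within 28 days prior to or after any dose of study vaccine". Exclusion 3 covers "Prior administration of an investigational coronavirus vaccine at any time". Exclusion 4 covers investigational products within 28 days. Exclusion 17 concerns only boosters planned for the future, and only in stage 4.

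The protocol also records that further boosters were available. Section 2.2.2 states "On March 29, 2022, the FDA authorized an additional booster dose (fourth dose) of mRNA vaccine for adults 50 years of age or older". It adds that bivalent formulations were authorized on 31 August 2022 "for use as a single booster dose at least two months following primary or booster vaccination".

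**The concern.** The interval in Table 1 runs from the last exposure. The interval in Inclusion 2 runs from completion of a primary series plus one booster. The two agree only for people who took nothing after that booster. For anyone who took a further authorized dose, the criteria drop from 16 weeks to 28 days. Section 5 grants no exemptions from the criteria, so their wording is what sites apply.

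Section 9.4.2 lists GMFR from baseline, by group and timepoint, among the analyses of the primary endpoint. Section 4.3 reports that a fourth mRNA dose raised neutralizing titers 9- to 10-fold. A subject who had such a dose a few weeks before Day 1 would plausibly enter with a raised baseline and show a smaller further rise. At stake are the per-arm baseline and GMFR, and whether the trial describes responses at the spacing it states.

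**Working it through.** **Step 1: run one person through the criteria.** Take someone whose primary series and first booster were complete more than 16 weeks before Day 1, and who then had an authorized further booster d days before Day 1.

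- Inclusion 2: met on its wording.
- Exclusion 1: not triggered (no infection).
- Exclusions 3 and 4: not triggered (authorized product, not investigational).
- Exclusion 7: not triggered once d is 29 or more.
- Exclusion 17: not triggered (past dose, not planned).
- Table 1: breached while d is below 16 × 7 = 112.

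The gap is therefore d = 29 to 111 days.

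**Step 2: is that window reachable?** Count from the authorization dates in Section 2.2.2:

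- Second booster, 29 March 2022: 29 days later is 27 April, and 112 days later is 19 July 2022.
- Bivalent booster, 31 August 2022: 29 days later is 29 September, and 112 days later is 21 December 2022.

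These are for doses given on the day of authorization; later doses move both dates later. Protocol versions 3.0, 4.0 and 5.0 are dated 29 April, 19 May and 21 September 2022, so the window was live around the time the later arms were added. The protocol gives no enrollment dates.

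**Step 3: reproduce the plan's precision figure.** Table 6 follows from exp(log GMT ± t(0.975, n−1) × SD/√n). At GMT 1000 and SD 1.0:

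- N = 100: (820.0, 1219.5), a half-width factor of 1219.5/1000 = 1.22.
- N = 50: (752.6, 1328.7), a factor of 1328.7/1000 = 1.33.

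Both match. At SD 0.5 the table gives 1104.3/1000 = 1.10 and 1152.7/1000 = 1.15.

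**Step 4: illustrate the shift in GMFR.** Let a share p of an arm have a baseline k times higher and an unchanged post-dose titer. The baseline GMT rises, and GMFR falls, by a factor of k^p. The documents give neither p nor k. The 9- to 10-fold rise in Section 4.3 serves as a rough upper bound for k.

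| Share p | k = 3 | k = 9 |
|---|---|---|
| 5% | 1.06 | 1.12 |
| 10% | 1.12 | 1.25 |
| 20% | 1.25 | 1.55 |

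If the post-dose titer also rises by √k, the exponent halves: at p = 10% the range becomes 3^0.05 to 9^0.05, or 1.06 to 1.12.

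**Step 5: the share at which the shift equals the half-width.** Solve p = h/ln k, with h the log half-width at SD 1.0: ln 1.2195 = 0.198 for N = 100 and ln 1.3287 = 0.284 for N = 50.

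| k | N = 100 | N = 50 |
|---|---|---|
| 2 | 29% | 41% |
| 4 | 14% | 21% |
| 9 | 9% | 13% |

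This comparison borrows the SD of titers for the log fold rise, for which the protocol gives no SD.

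**The case against.** The strongest reply is that Table 1 is itself part of the protocol. Section 10.1.9.4 makes any departure from the protocol a deviation, so a site that reads Table 1 would not dose someone boosted five weeks earlier. Other text points the same way: Section 4.3 speaks of a second boost after the primary series, and Section 5 expects people with a primary series and one boost. A lenient reader could also take the booster series in Inclusion 2 to include every booster received. This shows what was probably intended. It does not remove the conflict, because the list that decides eligibility says something else and sites may apply it differently.

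A second reply is that the per-protocol set could drop these subjects. Section 9.3 removes people ineligible at baseline, and on the wording of the criteria these people are eligible. They could be removed only if a breach of Table 1 were judged a deviation that affects the science. Section 9.4.2 makes the per-protocol analysis optional.

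The objections to a larger claim stand. A reader might infer that comparisons between stages or vaccine platforms are distorted because recent boosters became more common as stages opened. The documents do not support that:

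- The dates available are protocol version dates, not stage openings, and Section 1.1 allows stages to overlap.
- No cross-stage or platform comparison is specified, and Section 9.1 states that the trial tests no hypothesis.
- The March 2022 authorization was mainly for ages 50 and over, whereas stage 4 enrolls ages 18 to 49. For that stage the August bivalent is the only broad route.

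A reader might also infer bias between arms. Section 6.3.2 allocates equally within each stage, so such subjects are balanced across arms in expectation.

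**Conclusion.** The contradiction holds on the text alone. Table 1 and Inclusion 2 set different reference points for the vaccination interval, and people with a further authorized booster 29 to 111 days before Day 1 fall between them.

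The effect is a risk to per-arm baseline titers and GMFR, not a shown bias. Its direction follows from the protocol's own fourth-dose data. Its size cannot be fixed, because the affected share and the baseline excess are assumptions. At 10% affected and k from 3 to 9, the factor of 1.12 to 1.25 passes the N = 100 half-width of 1.22 only near the top of that range, and does not reach 1.33 at N = 50 (both at SD 1.0). A smaller SD would make the same shift matter more; a smaller k or a partly raised post-dose titer would make it matter less.

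GMFR is one summary of a primary endpoint that also covers response rate and titer magnitude. If the post-dose titer is unchanged, post-dose GMT does not move. Severity is therefore moderate. A reader might call this a defect that must be cured before any result can be used, but the documents do not support that.

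**What to change.** Reconcile Inclusion 2 with the Table 1 footnote, so that both state the same vaccination interval and the same dose from which it is counted. Which interval applies is for the study team to decide.

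For subjects already enrolled, derive time since the last COVID-19 vaccine dose before Day 1. Section 6.5 says that COVID-19 vaccination at any past time is captured in the database. Report how many subjects per arm do not meet the Table 1 interval, and show GMFR with and without them as a per-protocol or sensitivity analysis.

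The cost is one reconciled passage in the next amendment, one derived variable and one extra analysis. Depending on how the passages are reconciled, a few candidates may have to enroll later.

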1.2 Schedule of Activities (SOA)

Table 2: SOA for single dose

Study Day	D-28 to D-1	1	4	8 ^b	15	29	91	181	271	366	Illness/ Unsche duled Visit ^{k,m}	Early Terminati on Visit
Visit Number	00 ^a	1	1A	2	3	4	5	6	7	8		
Window (+/-)		0	1	1	2	2	7 ^m	14 ^m	14 ^m	28 ^m		
Informed Consent ^a	X											
Eligibility Criteria	X											
Medical History	X											
Vaccination		X										
Concomitant Meds	X	X	X ^j	X ^j	X ^j		X ^j					
Interim History		X	X	X	X	X	X	X	X	X	X	X
Physical Exam ^c - Targeted	X	X										(X)
Vital Signs ^c	X	X										(X)
Height/Weight (BMI) ^a	X											
Urine β-HCG ^d	X	X										
Memory Aid ^e	X	X	X									
Solicited AEs	X	X	X									
Unsolicited AEs	X	X	X	X	X							
MAAEs, SAEs, NOCMCs, AEs leading to withdrawal from the study and AESIs		X	X	X	X	X	X	X	X	X		X
Nasal swab for PCR & Sequencing ^f												(X)
Assays												
Serum for Serological Immunogenicity Assays ^g and Biomarker Testing ^l		34 ^l	4 ^l		34	34	34	34	34	34	4 ^l -34 ^m	34
PBMC Cellular Assays & Plasma ^{g,h}		64-70			64-70		64-70	64-70	64-70		64-70 ^m	64-70

(select sites only)												
Daily Volume (mL) ^{g,i}		98-104	4		98-104	34	98-104	98-104	98-104	34	4-104	98-104
Cumulative Volume (mL) over 56 day-period ^{g,i}		98-104	102-108		200-212	234-246	132-138	98-104	98-104	132-138		
Total Cumulative Volume (mL) ^{g,i}		98-104	102-108		200-212	234-246	332-350	430-454	528-558	562-592		

^a Optional screening visit – informed consent and screening activities can be a separate visit or combined with Day 1.

^b Telephone visit

^c Vital signs and targeted physical exam will be performed on screening and before vaccination otherwise, only as clinically indicated or based on interim medical history.

^d For subjects of childbearing potential, a urine pregnancy will be performed at screening. If enrollment occurs on a separate day, a repeat urine pregnancy test will be done within 24 hours of study vaccine administration and negative results confirmed prior to dosing.

^e The memory aid will be distributed at the Day 1 visit, queried for completion at the Day 8 telephone call and reviewed during an interview with the subject at the D15 visit and confirmed data recorded on the DCF.

^f Collect nasal swab for PCR (1-2). Swabs can be self-collected and visit done by phone. Sequencing will be performed on all Illness visit-confirmed SARS-CoV-2 specimens.

^g Inability (e.g., failure of venipuncture) to collect all baseline samples on Day 1 will not exclude the subject from further participation in this study as long as a minimum of baseline blood volume is collected (refer to the MOP for the protocol defined minimum number of required aliquots). Blood volume for PBMC varies depending on the type of tubes used for blood collection (refer to the MOP).

^h Selected sites will perform PBMC separation on selected subjects (refer to MOP for more guidance).

ⁱ Blood volumes for early termination visit are not included in the blood volume totals.

^j After vaccination on Day 1, immunosuppressant drugs, COVID-19 related prophylaxis and therapies as well as vaccines will be recorded. For any SAE occurring at any time during the study, all medications will be recorded.

^k If an unscheduled visit is performed to evaluate an adverse event, vital signs and targeted physical exam will be performed, as indicated. If, in the judgement of the site investigator, the event, occurring within 4 weeks after vaccination, is a case of suspected myocarditis and/or pericarditis, the site will coordinate an appropriate diagnostic workup to make a determination of probable or confirmed myocarditis and/or pericarditis which may include, but is not limited to, an ECG, cardiac troponin testing and referral to a cardiologist (directly, or through the emergency department or primary care clinic). The suspected myocarditis and/or pericarditis case should be reported to the DMID Medical Monitor within 24 hours of site awareness.

^l Serum for biomarker testing will be collected on Day 4 and stored for potential biomarker testing at a central laboratory and compared to testing of an aliquot from serum obtained on Day 1. If an unscheduled visit is related to a concern for myocarditis and/or pericarditis within 4 weeks after vaccination, a 4 mL SST will be collected and stored for potential biomarker testing at a central laboratory.

^m If a participant is planning to receive a COVID-19 booster outside the study, an unscheduled visit will be performed where safety and immunogenicity (collection of sera, plasma and PBMC) assessments will be performed. However, if that planned visit falls within twice the window for an upcoming visit (e.g +/- 14 days for

D 91, +/-28 days for D 181 and D 271, +/- 56 days for D 366) then it will occur and be documented as out of window for the planned upcoming scheduled visit (refer to MOP for more guidance).

Table 3: SOA for 2 doses

Study Day	D-28 to D-1	1	4	8 ^b	15	29	57	60	64 ^b	71	85	147	237	327	422	Illness/Unscheduled Visit ^{k,m}	Early Termination Visit
Visit Number	00 ^a	1	1A	2	3	4	5	5A	6	7	8	9	10	11	12		
Window (+/-)		0	1	1	2	2	3	1	1	2	2	7 ^m	14 ^m	14 ^m	28 ^m		
Informed Consent ^a	X																
Eligibility Criteria	X							X									
Medical History	X							X									
Vaccination		X						X									
Concomitant Meds	X	X	X ^j	X ^j	X ^j	X ^j	X ^j	X ^j	X ^j	X ^j							
Interim History		X	X	X	X	X	X	X	X	X	X	X	X	X	X	X	X
Physical Exam ^c – Targeted	X	X						X									(X)
Vital Signs ^c	X	X						X									(X)
Height/Weight (BMI) ^a	X																
Urine β -HCG ^d	X	X						X									
Memory Aid ^e		X	X	X				X	X	X							
Solicited AEs		X	X	X				X	X	X							
Unsolicited AEs		X	X	X	X	X	X	X	X	X	X						
MAAEs, SAEs, NOCMCs, AEs leading to withdrawal from the study and AESIs		X	X	X	X	X	X	X	X	X	X	X	X	X	X	X	X

Nasal swab for PCR & Sequencing ^f																	(X)	
Assays																		
Serum for Serological Immunogenicity Assays ^g and Biomarker Testing ^l		34 ^l	4 ^l		34	34	34 ^l	4 ^l		34	34	34	34	34	34	4 ^l -34 ^m	34	
PBMC Cellular Assays & Plasma ^{g,h} (select sites only)		64-70			64-70		64-70			64-70		64-70	64-70			64-70 ^m	64-70	
Daily Volume (mL) ^{g,i}		98-104	4		98-104	34	98-104	4		98-104	34	98-104	98-104	98-104	34	4-104	98-104	
Cumulative Volume (mL) over 56 day-period ^{g,i}		98-104	102		200	234	332	238		336	268	132-138	98-104	98-104	132			
Total Cumulative Volume (mL) ^{g,i}		98-104	102		200	234	332	336		434	468	566-596	664	762	796			

^a Optional screening visit – informed consent and screening activities can be a separate visit or combined with Day 1.

^b Telephone visit

^c Vital signs and targeted physical exam will be performed on screening and before vaccination otherwise, only as clinically indicated or based on interim medical history.

^d For subjects of childbearing potential, a urine pregnancy test will be performed at screening. If enrollment occurs on a separate day as screening, a repeat urine pregnancy test will be done within 24 hours of first study vaccine administration and repeated on day 57 prior to second study vaccine administration. Negative results must be confirmed prior to each dosing.

^e The memory aid will be distributed at the Day 1 and Day 57 visits, queried for completion at the Day 8 and Day 64 telephone calls and reviewed during an interview with the subject at the D15 and Day 71 visits and confirmed data recorded on the DCF.

^f Collect nasal swab for PCR (1-2). Swabs can be self-collected and visit done by phone. Sequencing will be performed on all Illness visit-confirmed SARS-CoV-2 specimens.

^g Inability (e.g., failure of venipuncture) to collect all baseline samples on Day 1 will not exclude the subject from further participation in this study as long as a minimum of baseline blood volume is collected (refer to the MOP for the protocol defined minimum number of required aliquots). Blood volume for PBMC varies depending on the type of tubes used for the blood collection (refer to the MOP).

^h Selected sites will perform PBMC separation on selected subjects (refer to MOP for more guidance).

ⁱ Blood volumes for early termination visit are not included in the blood volume totals.

^j After vaccination on Day 1, immunosuppressant drugs, COVID-19 related prophylaxis and therapies as well as vaccines will be recorded. For any SAE occurring at any time during the study, all medications will be recorded.

^k If an unscheduled visit is performed to evaluate an adverse event, vital signs and targeted physical exam will be performed, as indicated. If, in the judgement of the site investigator, the event, occurring within 4 weeks after each vaccination, is a case of suspected myocarditis and/or pericarditis, the site will coordinate an appropriate diagnostic workup to make a determination of probable or confirmed myocarditis and/or pericarditis which may include, but is not limited to, an ECG, cardiac troponin testing and referral to a cardiologist (directly, or through the emergency department or primary care clinic). The suspected myocarditis and/or pericarditis case should be reported to the DMID Medical Monitor within 24 hours of site awareness.

^lSerum for biomarker testing will be collected on Days 4 and 60 and stored for potential biomarker testing at a central laboratory and compared to testing of an aliquot of serum obtained on Days 1 and 57, respectively. If an unscheduled visit is related to a concern for myocarditis and/or pericarditis within 4 weeks after vaccination, a 4 mL SST will be collected and stored for potential biomarker testing at a central laboratory.

^mIf a participant is planning to receive a COVID-19 booster outside the study, an unscheduled visit will be performed where safety and immunogenicity (collection of sera, plasma and PBMC) assessments will be performed. However, if that planned visit falls within twice the window for an upcoming visit (e.g +/- 14 days for D 147, +/-28 days for D 237 and D 327, +/- 56 days for D 422) then it will occur and be documented as out of window for the planned upcoming scheduled visit (refer to MOP for more guidance).

Note Windows for subsequent visits should be based off the preceding vaccination visit.

If intercurrent SARS- CoV-2 infection occurs between the first and prior to the planned second study dose or if a COVID-19 vaccine is given outside the study between the first and prior to the planned second study dose, no second vaccination will be given. Participants who do not receive a second dose will revert to the schedule of activities for single dose participants.

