4.2 Scientific Rationale for Study Design

An open-label study will facilitate the need for rapid review and dissemination of study data for public health reasons. Safety findings are not expected to be dissimilar from Phase 1/2/3 studies conducted for similar vaccine constructs. Randomization will improve comparisons between the different arms. Each stage will contain an arm with the prototype vaccine with the exception of stage 4.

Selected arms will assess 2 study doses of vaccine candidates to assess if 2 doses provide a more durable response and more specific to variant viruses.

We chose the interval of 4 months since a recent study performed by our investigators showed that an interval of 3 months between primary series and boost had acceptable safety and immunogenicity responses.¹⁹

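### Table 3 (two-dose schedule) shows no PBMC draw at Day 327, but its three blood-volume rows count one, so the rows must be reconciled

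*Protocol*

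**What the plan says.** Protocol Section 1.2, Table 3, sets the visits for the two-dose arm. The late visits are Days "147 237 327 422". Five rows bear on blood volume.

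- The row "PBMC Cellular Assays & Plasma" (selected sites only) has 64-70 mL at Days 1, 15, 57, 71, 147 and 237, and again in the illness and early-termination columns. It is blank at Days 327 and 422.
- The serum row, from Day 71 on, reads "34 34 34 34 34 34 4 ^l -34 ^m 34", so serum at Day 327 is 34 mL.
- The daily volume row, from Day 71 on, reads "98-104 34 98-104 98-104 98-104 34 4-104 98-104", so Day 327 carries 98-104 mL and Day 422 carries 34 mL.
- The 56-day cumulative row ends "132-138 98-104 98-104 132" for Days 147 to 422.
- The total cumulative row ends "566-596 664 762 796" for the same visits.

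Table 2, the single-dose schedule, has PBMC 64-70 mL at Days 91, 181 and 271 and none at Day 366. Footnote i to both tables leaves early-termination blood out of the totals. Section 4.2 gives the reason for the two-dose regimen: "Selected arms will assess 2 study doses of vaccine candidates to assess if 2 doses provide a more durable response". Table 1 shows arm 3 (Beta + Omicron, second dose on Day 57) as the only two-dose arm. Arm 2 receives the same vaccine once.

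**The concern.** Within one table, the row that tells sites what to draw and the rows that add up what is drawn disagree about Day 327.

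Day 327 is 270 days after dose 2, and Table 2 draws PBMC at the corresponding single-dose visit, Day 271. If the PBMC row is followed, the last scheduled cellular sample in arm 3 is Day 237, 180 days after dose 2. The single-dose arms, including same-vaccine arm 2, would still have one at 270 days. An exploratory look at whether a second dose prolongs B- or T-cell responses could then not be made at 9 months. A PBMC sample that was never drawn cannot be recovered later. If the blank is what was meant, three rows of stated blood volumes are too high instead.

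**Working it through.** **Inputs** (all from Section 1.2). Serum, PBMC, daily and cumulative rows of Table 3; the same rows of Table 2; dose 2 on Day 57.

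**Formula.** Daily volume = serum + PBMC. Total cumulative = running sum of the daily volumes.

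**Step 1: reproduce the printed totals from the serum and PBMC rows as printed**, with PBMC at its lower bound of 64 mL.

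| Day | Serum | PBMC | Daily | Running total | Printed total |
|---|---|---|---|---|---|
| 1 | 34 | 64 | 98 | 98 | 98-104 |
| 4 | 4 | none | 4 | 102 | 102 |
| 15 | 34 | 64 | 98 | 200 | 200 |
| 29 | 34 | none | 34 | 234 | 234 |
| 57 | 34 | 64 | 98 | 332 | 332 |
| 60 | 4 | none | 4 | 336 | 336 |
| 71 | 34 | 64 | 98 | 434 | 434 |
| 85 | 34 | none | 34 | 468 | 468 |
| 147 | 34 | 64 | 98 | 566 | 566-596 |
| 237 | 34 | 64 | 98 | 664 | 664 |
| 327 | 34 | none | 34 | **698** | **762** |
| 422 | 34 | none | 34 | **732** | **796** |

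Every lower bound agrees through Day 237. With PBMC at 70 mL the Day 147 total is 596, also as printed. The totals then fail: 762 − 698 = 64 and 796 − 732 = 64, exactly one PBMC draw.

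**Step 2: add PBMC at Day 327.** Daily = 34 + 64 to 34 + 70 = 98-104, as printed. Totals are 664 + 98 = 762 and 762 + 34 = 796, as printed. At 70 mL the totals are 700 + 104 = 804 and 804 + 34 = 838. Table 3 prints only the lower bounds here.

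**Step 3: leave PBMC out at Day 327.** Daily = 34. Totals are 698 to 700 + 34 = 734 at Day 327, and 732 to 734 + 34 = 768 at Day 422.

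**Step 4: the 56-day row.** It prints 98-104 at Day 327, again serum plus PBMC. Its 132 at Day 422 equals 98 + 34, so it also counts a full draw at Day 327. Without the draw the two cells would be 34 and 34 + 34 = 68.

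**Step 5: control on Table 2.** The same running sum gives 98, 102, 200, 234, 332, 430, 528, 562 at 64 mL and 104, 108, 212, 246, 350, 454, 558, 592 at 70 mL. Every printed total in Table 2 is reproduced at both bounds.

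**Step 6: matching visits.** 327 − 57 = 270 days and 271 − 1 = 270 days. The late PBMC visits after the last dose are at 90, 180 and 270 days in Table 2 (Days 91, 181, 271). Table 3 as printed has them at 90 and 180 days only (Days 147, 237). Neither schedule draws PBMC at 365 days (Days 366 and 422), so the loss is one of three late cellular visits.

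Early-termination blood cannot explain the 64 mL, because footnote i excludes it.

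**The case against.** The strongest objection is that the blank may come from reading the PDF. Table 3 is visibly disturbed elsewhere: the marks for the second vaccination fall under Day 60 although dose 2 is on Day 57, and the concomitant-medication row stops early. A lost entry cannot be excluded without the source. That stands, and it is why the fix begins with the PDF. Against it, the PBMC row has as many cells as the serum and volume rows and lines up with them at every other visit, including the illness and early-termination columns. It has six scheduled entries against seven daily volumes of 98-104 mL. A shifted row would move an entry without removing it.

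It is also fair to say that sites do not work from this cell alone. Footnote h refers them to the manual of procedures for PBMC, and Section 8.1.2 refers to an immune monitoring plan. Neither is at hand, and either may settle practice. For the same reason, one cannot conclude from the protocol that some sites will draw and others will not.

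A reader might infer that arm 3 can no longer answer the durability question for which it exists. The documents do not support that. Section 9.2.2 states the primary objective in terms of serum antibody titers, and the 34 mL serum draw at Day 327 is printed. Section 4.2 does not say that the durable response it has in mind is cellular. The cellular endpoints are exploratory, in subsets of samples and mostly at unnamed time points (Section 3), and Section 9.1 disclaims any specific hypothesis test. No month-9 cellular comparison is promised.

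**Conclusion.** The inconsistency holds. At Day 327 the PBMC row and three volume rows of Table 3 differ by exactly one draw of 64-70 mL. The volume rows and the parallel visit in Table 2 suggest an omitted entry, but the protocol does not settle which row is intended. Nor does anything in it present the blank as a deliberate choice.

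The consequence is limited. If the PBMC row governs, arm 3 lacks the exploratory cellular sample at 270 days after the last dose, one of three late cellular visits. The 100 subjects of arm 3 are not the number affected. PBMC is collected from selected subjects at selected sites, and the subset size is not stated. Arm 3 subjects who miss dose 2 revert to the single-dose schedule, which has PBMC at Day 271. The primary humoral endpoint is unaffected. If the volume rows govern, no sample is lost and only one cell is wrong.

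The weight is minor to moderate. The conclusion assumes that the blank is in the source PDF and that the manual of procedures has not already resolved it.

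**What to change.** Check the Day 327 cell of the PBMC row in the source PDF. If it is blank there, reconcile the rows in one of two ways.

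1. Enter PBMC 64-70 mL at Day 327. This changes one cell, adds no blood beyond the daily volume already stated, and matches Day 271 in Table 2.
2. Keep the blank and correct the volume rows: daily 34 mL at Day 327; 56-day 34 mL at Day 327 and 68 mL at Day 422; total 698-734 mL at Day 327 and 732-768 mL at Day 422. State that no 9-month cellular comparison with arm 3 will be made.

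Either way, bring the manual of procedures into line. The cost is an editorial correction to one table.
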